#### INTRODUCTION

Since its introduction 27 years ago, endoscopic ultrasound-guided fine needle aspiration (EUS-FNA) has revolutionized the diagnostic approach to pancreatic masses and has become the first diagnostic test to establish a correct diagnosis in patients with suspicious pancreatic solid lesion. EUS-FNA represents now the standard of care for the pathological diagnosis of solid pancreatic masses, and has a sensitivity and a specificity of 85%–89% and 96%–99%, respectively. Needles of different size have been used, ranging from 19 Gauge to 25 Gauge, despite the strongest evidences is for the 22 and the 25 Gauge needles. The availability of rapid on-site evaluation (ROSE) to assess specimens' adequacy by a cytopathologist during EUS-FNA improves diagnostic accuracy of about 10 to 15%, but high costs and the lack of availability of ROSE in many centers, even the referral ones, have limited the widespread utilization of the EUS-FNA procedures. For these reasons in recent years, new needles have been designed (i.e. cutting tip or a side-slot in the distal portion of the needle) to obtain samples suitable for histological evaluation (endoscopic ultrasound-guided fine needle biopsy [EUS-FNB]). These new needles allow the macroscopic onsite evaluation (MOSE) of the quality of samples by the endoscopist, who can decide whether or not to perform additional biopsies. Various EUS-FNA techniques have been described, but the correct methods remain debatabl. Most of the studies have compared EUS-FNA with standard suction (10-20 ml negative suction pressure) versus the "slow-pull" EUS-FNA technique (pulling the stylet while moving the needle within the lesion), but final results were conflicting and ranged from clear advantage of the slow-pull approach to no difference between the two techniques. In the studies that showed advantages of the slow-pull technique, most of the gain was related to a significant decrease of the bloodiness of the specimens, which made the cytological reading easier to be accomplished as compared to more bloody specimens obtained with the suction technique. The interference of bloodiness with the cytological evaluation is a well-known phenomenon. On the other hand, data on the amount of blood gathered during EUS-FNB performed using the two different techniques and its interference with the performance of both slow pull and standard suction techniques in patients with pancreatic solid lesions are limited. The aim was to design a randomized controlled study to compare the amount of bloodiness of the specimens acquired by the slow-pull technique with those gathered by using the standard suction technique during EUS-FNB in patients with solid pancreatic masses. Secondary aims were the effect of blooding on the performance of the two techniques with regards to sensitivity, specificity, and diagnostic accuracy.

#### Materials and methods

A Randomized, multicenter study comparing the slow-pull technique with the standard suction technique during EUS-FNB in patients with pancreatic solid lesions. The study involved three referral centers for pancreatico-biliary diseases: the Gastroenterology and Endoscopy Unit. ARNAS Civico-Di Cristina-Benfratelli Hospital, Palermo, Italy; the Gastroenterology and Endoscopy Unit. Marche Polytechnic University, Ospedale A. Murri, Fermo, Italy; the Gastroenterology Unit. AUSL Bologna, Bellaria-Maggiore, Bologna, Italy.

The protocol was approved by the institutional medical ethical committee at each participating institution and written informed consent was obtained from all patients for participation in the study.

All consecutive patients with a newly diagnosed pancreatic solid lesions suitable for EUS-guided tissue acquisition were considered for enrollment. Inclusion criteria were: age >18 years old; solid pancreatic lesion on imaging MRI and/or CT-scan referred for tissue acquisition; lesion that can be visualized with EUS and needle puncturing can be technically feasible; able to sign informed consent. Patients were excluded in the presence of at least one following criteria: <18 years-old, pancreatic cystic lesions, extra-pancreatic lesions or inaccessible/non-visualizable lesions, previous gastrectomy, international normalized ratio > 1.5, impossibility to suspend anticoagulant therapy, platelet count < 50.000 cells/cubic millimeter, severe or unstable clinical conditions that contraindicated EUS procedure, pregnancy, inability to give informed consent, and refusal to participate to the study. Written informed consent was obtained from all patients before the procedure.

All the EUS procedures were carried out by A skilled endosonographer with the patients under conscious sedation or deep sedation according to the anesthesiological guidelines approved in each participating center. All EUS-FNB were done using a 20 Gauge needle (EchoTip ProCore 20G with ReCoil StyletTM, Cook Medical, Bloomington, IN, USA). The ReCoil Stylet's has an automatic recoiling capability designed to help users to manage more easily the stylet, thus minimising the risk of contamination. Before puncturing, color doppler examination was performed to exclude the presence of interposing vessels. The needle tip was sharpened by withdrawing the stylet of approximately 2 mm, and then it was advanced into the lesion under real-time EUS guidance. In patients randomized to the stylet slow-pull techniques, 15 to-and-fro movements within the lesion were performed while gently pulling the needle stylet slowly and continuously upwards. In patients randomized to the standard suction technique, 15 to-and-fro movements within

the lesion were performed using a 10-mL suction syringe. In both sampling procedures the fanning technique was used to maximized sample acquisition. Tissue samples were expelled onto slides by reinserting the stylet and the visible core was physically lifted off the slides placing it into a formalin vial for histological evaluation. For the macroscopic adequacy, the endosonographer evaluated for the presence of a visible core defined as a worm-like material whitish/yellowish or red, not including fluid-like specimens in the formalin vial, which was judged to be adequate to perform a pathological analysis. The pathologists were "blinded" on which group the vials received were belonging to.

Randomization was performed using random sequences generated by a computer and then closed in consecutive numbered envelopes.

Data on patients' and lesions' characteristics, degree of the blood contamination of the specimen, sensitivity, specificity and diagnostic accuracy of the two techniques; adverse events related to the procedures were collected and entered in an electronic database in order to carry out the final statistical analysis.

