#### **Outcome measures**

The primary end point of the study was the degree of blood contamination of the collected specimens in patients with pancreatic solid lesions who underwent EUS-FNB using the 20Gauge Procore Needle and the slow pulling or the standard aspiration techniques. Secondary outcomes were technical success, comparison of the performance of the two techniques during EUS-FNB in terms of sensitivity, specificity, positive predictive value (PPV), negative predictive value (NPV), and diagnostic accuracy, and occurrence of adverse events.

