#### **Outcome Definitions**

The degree of blood contamination of the specimen was based on the pathologist evaluation of the formalin fixed and paraffin embedded (FFPE) tissue samples and defined as significant when a large amount of blood cells made pathological diagnosis difficult to be made. On the other hand, blood contamination of the specimen was defined as not significant when no or only few blood cells were present without any influence on the pathological diagnosis.

Sensitivity was defined as the true positive rate whereby the test was the final cytologic diagnosis, Specificity as the true negative rate (proportion of actual negatives that are correctly identified as such), PPV was defined as the number of true positive divided the number of positive calls (true positive and false positive), NPV was defined as the number of true negative divided the number of negative calls (true negative and false negative). Diagnostic accuracy was defined as the ratio between the sum of true positive and true negative values divided by the total number of masses.

Technical success was defined as the capability of sampling the target lesion associated with the presence of a visible core, according to endosonographer's judgment, potentially useful for the final pathological analysis.

Adverse events were defined based on the criteria expressed by Cotton et al. [Cotton PB. Gastrointest Endosc 2010;71:446-54]

Samples positive for malignancy were considered diagnostic for malignancy, while in patients with negative EUS-FNB, surgical specimen evaluation, results of other diagnostic investigations and/or a clinical follow-up of at least 6 months were used to establish the definitive diagnosis.

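### Technical success is scored only by the unblinded operator and needs no histological confirmation, although blinded pathologists already read the specimens

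*Combined protocol and SAP*

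**What the plan says.** Outcome measures lists technical success first among the secondary outcomes: "Secondary outcomes were technical success, comparison of the performance of the two techniques during EUS-FNB". Outcome Definitions describes it as follows: "Technical success was defined as the capability of sampling the target lesion associated with the presence of a visible core". The same sentence names the assessor and the standard: "the presence of a visible core, according to endosonographer's judgment, potentially useful for the final pathological analysis".

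Materials and methods gives the macroscopic criterion, a "visible core defined as a worm-like material whitish/yellowish or red, not including fluid-like specimens in the formalin vial", and adds a further condition: "which was judged to be adequate to perform a pathological analysis". It also states who did the procedures: "All the EUS procedures were carried out by A skilled endosonographer". The only blinding described is that of the pathologists: "The pathologists were 'blinded' on which group the vials received were belonging to". Their reading is defined for blood contamination, "based on the pathologist evaluation of the formalin fixed and paraffin embedded (FFPE) tissue samples", and they supply the diagnosis. No item records whether tissue was present.

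Results reports technical success as a comparison of the arms: 96% with slow-pull and 94% with suction, not significant.

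**The concern.** Three features combine.

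- **The assessor knows the arm.** Whoever pulls the stylet or attaches the syringe cannot be blind to the technique. No independent macroscopic assessor is described.
- **The criterion is sensitive to blood.** Red material is acceptable and only fluid-like material is ruled out. The Introduction and the sample-size premise both expect suction to give bloodier specimens, so the criterion is not independent of the effect under study.
- **Nothing confirms the judgement.** The added adequacy condition is the same operator's opinion. A success stands whatever the section later shows.

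The macroscopic score can therefore differ from true tissue yield, and by a different amount in each arm. At stake is whether 96% against 94% can be read as similar tissue yield, or only as similar operator opinion.

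**Working it through.** **Inputs (all from Results, 55 patients per arm).** Technical success: 96% slow-pull, 94% suction, 95% overall. Malignant diagnoses: 50 and 48. True negatives: 1 and 5. False negatives: 4 and 2. Not-significant blood contamination: 85 patients, 80% and 74%.

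**1. Reproduce the reported figure.** 53/55 = 96.4% and 52/55 = 94.5% (printed as 94%, so apparently truncated). Overall, 105/110 = 95.45%. Fisher's exact test gives p = 1.00, which agrees with the printed non-significance.

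**2. Does a blinded reading exist for everyone?** Blood: 44/55 + 41/55 = 85/110. Diagnosis: 50 + 1 + 4 = 55 for slow-pull and 48 + 5 + 2 = 55 for suction, 110 in total. Both use full denominators, so a pathology reading appears to exist for all randomised patients, including the 5 technical failures. Because the false negatives are counted separately, the 98 malignant diagnoses are positive EUS-FNB readings.

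**3. Bound the histological yield.** Tissue presence is not reported, so only limits can be given.

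| Assumption | Slow-pull | Suction | Extreme pairs (Fisher p) |
|---|---|---|---|
| Only malignant readings prove tissue | 50 to 55 (90.9% to 100%) | 48 to 55 (87.3% to 100%) | 55 vs 48: 0.013; 50 vs 55: 0.057 |
| Benign histology also proves tissue | 51 to 55 (92.7% to 100%) | 53 to 55 (96.4% to 100%) | 55 vs 53: 0.50; 51 vs 55: 0.12 |

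Under the first assumption the difference, slow-pull minus suction, lies between -5/55 = -9.1 and +7/55 = +12.7 percentage points. Under the second it lies between -4/55 = -7.3 and +2/55 = +3.6 points, and no combination reaches p < 0.05.

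**4. How much suction misclassification would matter?** Hold slow-pull at 53/55. Six tissue-free suction successes give 46/55 (p = 0.052) and seven give 45/55 (p = 0.029), so seven are needed for p < 0.05. But 48 malignant readings mean suction cannot fall below 48/55, a drop of four from 52, where p = 0.16. If benign histology proves tissue, suction cannot fall below 53/55.

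**5. Do operator and pathologist agree?** The operator's counts are 53 and 52. Correct histological diagnoses are 50 + 1 = 51 and 48 + 5 = 53, so the order reverses. Since 53 exceeds 52, at least one suction patient scored as a technical failure had a diagnostic specimen, provided each diagnosis came from the study specimen. The operator's score is then an imperfect proxy for usable tissue.

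**Check on the inputs.** These arm counts give sensitivity 50/54 = 92.6% for slow-pull and 48/50 = 96.0% for suction, and accuracy 51/55 = 92.7% and 53/55 = 96.4%. Results prints 96 vs 93% for both, with slow-pull first. The two must be reconciled. If the count labels were the ones swapped, the bounds in step 3 would swap arms and the inference in step 5 would fall.

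**The case against.** The strongest reply is that technical success is meant to be a procedural, macroscopic measure. The Introduction presents on-site inspection by the endoscopist as a feature of these needles, and pathological performance is already compared through sensitivity and accuracy on blinded readings. Red colour alone does not score a success, because the operator must also judge the core adequate. The blinded blood reading differs little (44/55 vs 41/55, p = 0.65), and suction scored slightly lower on technical success, not higher.

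Most of this stands. The measure is legitimate as a description of the procedure, and the adequacy condition narrows the criterion. What it does not answer is that the adequacy judgement is also unblinded, while the outcome is tested between arms. Sensitivity and accuracy do not replace a yield measure either, since a false negative can occur with or without tissue.

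A reader might infer that red cores are clot, that suction is therefore inflated, and that a large yield deficit lies behind 96% vs 94%. The documents do not support this. They never mention clot and give no rate of tissue-free cores. Operator expectation, which the sample-size premise aligns with slow-pull, could act in the opposite direction. A confirmed suction yield as low as 85% would contradict the 48 malignant readings (87.3%). If benign histology proves tissue, there is more room for tissue-free samples in slow-pull (4) than in suction (2).

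**Conclusion.** The point holds as a minor design weakness in one secondary outcome. An unblinded, blood-sensitive judgement without histological confirmation is used to compare the arms, although blinded pathologists read the same material. Misclassification that differs by arm is possible; neither its direction nor its size is established.

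The Results limit it to the ranges in the table. These ranges assume that a malignant reading proves tissue, that diagnoses came from the study specimens, and that the arm counts are as printed. They bound the presence of tissue, not of an intact core, which could be less frequent. Whether benign histology proves tissue is the assumption that changes the range most. The primary endpoint is the blinded pathologists' reading and is not affected.

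**What to change.** In Outcome Definitions, base the between-arm comparison of tissue yield on a yes/no item, tissue core present on the FFPE section. The blinded pathologists record it for all randomised patients, with 55 per arm as the denominator. Keep the operator's visible-core judgement as a descriptive macroscopic measure. Report by arm how many visible cores had no tissue on histology.

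The cost is one added item on the pathology form, with no new assessors or procedures. The success rate may be lower than the operator's. For the patients already reported, the item could be added by re-reading the slides if they were kept, which the documents do not state. If not, describe the reported 96% vs 94% as operator-assessed macroscopic success and not as tissue yield.

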#### **Outcome measures**

The primary end point of the study was the degree of blood contamination of the collected specimens in patients with pancreatic solid lesions who underwent EUS-FNB using the 20Gauge Procore Needle and the slow pulling or the standard aspiration techniques. Secondary outcomes were technical success, comparison of the performance of the two techniques during EUS-FNB in terms of sensitivity, specificity, positive predictive value (PPV), negative predictive value (NPV), and diagnostic accuracy, and occurrence of adverse events.

#### **Outcome Definitions**

The degree of blood contamination of the specimen was based on the pathologist evaluation of the formalin fixed and paraffin embedded (FFPE) tissue samples and defined as significant when a large amount of blood cells made pathological diagnosis difficult to be made. On the other hand, blood contamination of the specimen was defined as not significant when no or only few blood cells were present without any influence on the pathological diagnosis.

Sensitivity was defined as the true positive rate whereby the test was the final cytologic diagnosis, Specificity as the true negative rate (proportion of actual negatives that are correctly identified as such), PPV was defined as the number of true positive divided the number of positive calls (true positive and false positive), NPV was defined as the number of true negative divided the number of negative calls (true negative and false negative). Diagnostic accuracy was defined as the ratio between the sum of true positive and true negative values divided by the total number of masses.

Technical success was defined as the capability of sampling the target lesion associated with the presence of a visible core, according to endosonographer's judgment, potentially useful for the final pathological analysis.

Adverse events were defined based on the criteria expressed by Cotton et al. [Cotton PB. Gastrointest Endosc 2010;71:446-54]

Samples positive for malignancy were considered diagnostic for malignancy, while in patients with negative EUS-FNB, surgical specimen evaluation, results of other diagnostic investigations and/or a clinical follow-up of at least 6 months were used to establish the definitive diagnosis.

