# **Statistical Analysis**

The sample size was calculated based on the results of a previous study [Nakai Y. Dig Dis Sci. 2014;59:1578-85] that showed that blood contamination of the specimen was lower with the stylet slow-pull technique as compared with the standard suction technique (25% vs 70%), with a consequent increase in the diagnostic accuracy. Based on these data we calculated for a difference of 25%, at a power of 80% and an alpha of 0.05 (two-sided test), a final sample size of 110 patients (55 patients in each group). Continuous variables will be reported as mean ± standard deviation (SD). Categorical variables will be presented as numbers and percentage and will be compared either using the chi-square test (with Yates' correction when appropriate) or Fisher exact test.

Statistical was conducted using the Fisher's exact test for categorical variables and the Mann–Whitney U-test for continuous variables. Sensitivity, specificity, positive predictive value (PPV), negative predictive value (NPV), and overall diagnostic accuracy for each arm were investigated by comparing the results with the definitive diagnosis. Statistical tests were considered

significant at a corresponding p value of <0.05. Data handling and analyses were done with SPSS 14.

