#### RESULTS

From May 2017 to May 2018, a total of 182 consecutive patients were screened for participation in this study, of whom 72 were excluded, while 110 patients constituted the study cohort and were randomized to one of two groups: stylet slow-pull technique (55 patients) and standard suction technique (55 patients) as showed in figure 1. Overall, there were 49 male (44.5%) and 61 female (55.5%), with a mean age of 70.9±11.3 years. Patients' and lesions' characteristics are shown in Table 1 and appeared similar in both groups. The majority of lesions were located in the head of the pancreas (72 lesions corresponding to 65.5%) with similar rates in slow-pull group (69%) and in the standard suction group (62%). No difference in mean size of the lesions was found between the two groups(35.9±19.9 vs 37.6±14.1 cm; p=ns).

Technical success was achieved in 95% of patients (slow pull technique 96% vs standard suction technique 94%, p=ns) with a not-significant blood contamination of the specimen in 85 patients (overall 77.3%: slow-pull 80% vs standard suction 74%, p=ns). A diagnosis of malignancy was obtained in 98 cases as showed in Table 2. Fifty were in the slow-pull group and 48 in the standard suction group. In 6 patients (1 in the slow-pull and 5 in the standard suction group) with a benign histological diagnosis at EUS-FNB the definitive diagnosis was chronic pancreatitis. Thus, these patients were considered true negative. Finally there were 6 false negative cases (4 in the slow pull technique group and 2 in standard suction group). Comparing the two groups (Table 3), the sensitivity, specificity, negative likelihood ratio, positive likelihood ratio, and diagnostic accuracy were 96 vs 93%, 100% vs 100%, 0.04 vs 0.07, "infinity" in both, and 96 vs 93%, respectively without any statistical difference between them. No procedure-related adverse events were observed in the two groups.

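### A positive EUS-FNB is its own reference standard, so no false positive can be recorded and specificity and PPV are fixed at 100% in both arms

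*Combined protocol and SAP*

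**What the plan says.** Outcome measures lists, as secondary outcomes on which the two techniques are to be compared, "sensitivity, specificity, positive predictive value (PPV), negative predictive value (NPV), and diagnostic accuracy". Statistical Analysis says that these measures and "overall diagnostic accuracy for each arm were investigated by comparing the results with the definitive diagnosis".

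Outcome Definitions then fixes what the definitive diagnosis is: "Samples positive for malignancy were considered diagnostic for malignancy, while in patients with negative EUS-FNB, surgical specimen evaluation", other diagnostic investigations and/or at least 6 months of follow-up are used. Only negatives go to an outside reference. The same section states that "PPV was defined as the number of true positive divided the number of positive calls (true positive and false positive"), so the definition has a false-positive term.

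RESULTS reports that "the sensitivity, specificity, negative likelihood ratio, positive likelihood ratio, and diagnostic accuracy were 96 vs 93%, 100% vs 100%, 0.04 vs 0.07", with an infinite positive likelihood ratio in both arms and 96 vs 93% for accuracy, "respectively without any statistical difference between them". The positive likelihood ratio is reported there but is not among the planned outcomes.

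**The concern.** For a patient with a positive sample, the index test and the reference are the same thing and cannot disagree. A false positive therefore cannot be recorded however often a technique produces one. Two planned comparisons have only one possible result, and the PPV definition contains a cell that the reference rule never fills.

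A reader of RESULTS would take equal specificity as a finding that the techniques perform alike. It would have been printed whatever the techniques did. Sensitivity and accuracy can still differ between arms, but both rest on the unstated assumption that every positive is a true positive.

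**Working it through.** **Inputs, all from RESULTS.** Each arm has 55 patients. Malignant on EUS-FNB: "Fifty were in the slow-pull group and 48 in the standard suction group". True negatives: "In 6 patients (1 in the slow-pull and 5 in the standard suction group) with a benign histological diagnosis at EUS-FNB" had chronic pancreatitis as the definitive diagnosis. False negatives: 4 slow-pull, 2 suction.

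**False-positive cell by subtraction.**
- Slow-pull: 55 − 50 − 1 − 4 = 0.
- Suction: 55 − 48 − 5 − 2 = 0.

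**Reproducing the reported figures.** With FP = 0 by rule:
- Specificity = TN/(TN + FP): 1/1 = 100% and 5/5 = 100%, as printed.
- PPV = TP/(TP + FP): 50/50 = 100% and 48/48 = 100%. The RESULTS text gives no PPV, and Tables 2 and 3 are not available to check.
- Positive likelihood ratio = sensitivity/(1 − specificity): division by zero, so infinite in both arms, as printed.
- NPV = TN/(TN + FN) contains no FP term and is unaffected.

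**What the rule costs.** These are exact (Clopper-Pearson) 95% intervals.
- PPV, had every positive been verified and none found false: 50/50 gives 92.9% to 100%; 48/48 gives 92.6% to 100%. Under the rule these intervals cannot be claimed.
- Specificity: 1/1 gives 2.5% to 100%; 5/5 gives 47.8% to 100%. The most extreme split (0/1 vs 5/5) has Fisher p = 1/6 = 0.167, so no test at these counts could reach 0.05 even with a perfect reference.

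**How many false positives might be hidden.** The documents do not say. Assume that the Introduction's EUS-FNA specificity of 96% to 99% applies to EUS-FNB. With 6 true negatives, the expected whole-trial count is 6 × 0.01/0.99 = 0.06 to 6 × 0.04/0.96 = 0.25. This is illustrative only, because the reference standard behind the 96% to 99% is not visible.

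**Sensitivity to one false positive in an arm.** This is an assumption; the true number may be 0, and one is already 4 times the upper expectation. One positive moves from TP to FP:

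| | Slow-pull | Suction |
|---|---|---|
| Specificity | 1/2 = 50.0% | 5/6 = 83.3% |
| PPV | 49/50 = 98.0% | 47/48 = 97.9% |
| Positive likelihood ratio | 0.9245/0.5 = 1.85 | 0.9592/0.1667 = 5.76 |
| Sensitivity | 50/54 = 92.59% to 49/53 = 92.45% | 48/50 = 96.00% to 47/49 = 95.92% |
| Accuracy | 51/55 = 92.7% to 50/55 = 90.9% | 53/55 = 96.4% to 52/55 = 94.5% |

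The large moves in specificity and the likelihood ratio mostly reflect the 1 and 5 benign patients. Sensitivity moves by about 0.1 point and accuracy by 1.8 points.

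**Arm labels are provisional.** From the counts, slow-pull vs suction, sensitivity is 92.6% vs 96.0%, the negative likelihood ratio is 4/54 = 0.07 vs 2/50 = 0.04, and accuracy is 92.7% vs 96.4%. RESULTS prints 96 vs 93%, 0.04 vs 0.07 and 96 vs 93%. Exchanging the two arms' full counts reproduces all three printed pairs. Exchanging only the false negatives does not: 48/(48 + 4) = 92.3%, a negative likelihood ratio of 4/52 = 0.08, and arm totals of 53 and 57. The documents do not show whether the counts or the percentages are right.

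**The case against.** Accepting positive histology as definitive is a practical choice, and false positives are rare. On the documents' own figures the consequence is small. Specificity could not have been compared with six benign patients. A PPV difference was not realistically detectable either: with 50 and 48 verified positives and all false positives in one arm, Fisher p < 0.05 needs 6 in slow-pull (p = 0.027; 5 gives 0.056) or 5 in suction (p = 0.025; 4 gives 0.054), against an expected 0.25 at most. The one-false-positive swings in specificity and likelihood ratio look more dramatic than they are likely. The arm-order discrepancy is a separate matter from the reference rule.

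Most of this stands, and it is why the point is minor. A verified reference would have yielded a usable PPV estimate per arm, though not a powerful comparison. None of it turns a value fixed by definition into an observation, so reporting it as a comparison remains wrong. The arm-order discrepancy does not affect the zero false-positive cell. It belongs here only because any corrected table of these measures would carry it forward.

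**Conclusion.** The point holds and is minor. Under the reference rule, specificity and PPV are 100% and the positive likelihood ratio is infinite in any arm with at least one benign patient and one positive. Both arms met that condition. These measures cannot discriminate between the techniques, and the equal specificities are not evidence of similarity.

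This rests only on the written rule and on the absence of any provision elsewhere in the documents for verifying a positive. The size of any hidden error is unknown: no false positive is shown, few would be expected, and no arm is shown to be favoured. The primary endpoint of blood contamination is unaffected. The no-difference statement for sensitivity and accuracy stands whichever way the arms are labelled (Fisher p = 0.68 for each), subject to the assumption that all 98 positives are true.

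**What to change.** 1. Keep the prespecified measures, but label specificity, PPV and the positive likelihood ratio as fixed by the reference rule. Report them descriptively per arm with no between-arm test, and remove specificity and this ratio from the results said to show no statistical difference.
2. State that sensitivity and accuracy assume every positive is a true positive, and give exact 95% intervals. From the counts as printed, with provisional arm labels: sensitivity 82.1% to 97.9% (slow-pull) and 86.3% to 99.5% (suction); accuracy 82.4% to 98.0% and 87.5% to 99.6%.
3. Before publishing any arm-specific figure, reconcile the RESULTS counts with the printed percentages against source data.
4. If surgical pathology or follow-up already exists for some positives, report discordant cases as a descriptive sensitivity analysis only, with the number verified per arm. State the limitation that unchecked positives remain true positives by rule and that the checked share may differ by arm.

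Items 1 to 3 need no new patient data. Item 4 depends on data the documents do not show to exist, and it carries partial-verification bias. The price is that specificity and PPV can no longer be presented as compared outcomes.
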